NOTE: The first occurrence of some abbreviations is not spelled out in the document (e.g., units of measure).

SYNOPSIS

STAAR Surgical Company Study #CP18-02	
Revision chronology:	Rev #2, 2019.June.10
Title:	Post-Approval Study of the Visian Toric Implantable Collamer Lens
Type of study:	Post-approval study (PAS)
Number of study centers and subjects:	The study will enroll and implant at least 124 eligible subjects (up to 248 eyes, with 124 being primary) at 6-8 clinical sites in the US, to ensure that at least 100 subjects (assuming an overall attrition of 10% per year) will be available for evaluation at 24 months after implantation.
Objective(s):	The objective of this PAS is to evaluate the long term (i.e. 24 months) clinical performance of the Visian® Toric Implantable Collamer® Lens (ICL) for Myopia (TICL) with respect to rotational stability, refractive and visual outcomes, and ocular adverse event (AE) rates.
Study design	
This is a prospective, multicenter, open-label, single arm, post approval study. Up to 124 subjects who meet all eligibility criteria will be offered consecutive enrollment in the study.
 
It is intended that each enrolled subject will undergo bilateral implantation with the TICL. If only one eye of a given subject meets all of the inclusion and exclusion criteria, or the subject desires surgery in only one eye and that eye meets all of the inclusion and exclusion criteria, then that eye will be the primary eye. If both eyes of a given subject meet all of the inclusion and exclusion criteria, and the subject desires surgery in both eyes, then the eye with the greater magnitude of manifest refraction cylinder will be designated as the primary eye. If both eyes of a given subject meet all of the inclusion and exclusion criteria and the refractive cylinder of the eyes are equal, then the right eye will be designated as the primary eye.
 
A minimum of 14 subjects requiring a Toric ICL cylinder power of 3.5 or 4.0 diopters will be enrolled.
 
Postoperatively, subjects will return for visits at regularly scheduled intervals through 24 months after surgery (see App A).

Subject Population	Investigators will all have prior clinical experience with the STAAR Surgical Implantable Collamer Lens. Subjects will be selected from each clinical site’s patient population. Patients meeting all of the following criteria will be considered suitable study subjects. All subjects enrolled in this clinical study will meet the requirements under the indications for use outlined in the package insert directions for use (DFU) for the FDA approved lenses and additional eligibility criteria. (refer below)

	
Inclusion Criteria (each eye to be implanted)
 
1. Subjects 21 through 45 years old at time of surgery.2. Moderate to high myopia with spherical equivalent ranging from -3.0 D to \leq -15.0 D (in the spectacle plane) and cylinder in the range of 1.0 D to 4.0 D (in the spectacle plane).3. Stable refractive history within 0.5 D for both spherical equivalent and cylinder for 1 year prior to implantation.4. Anterior chamber depth (ACD) 3.0 mm or greater, when measured from the corneal endothelium to the anterior surface of the crystalline lens.5. Meet minimum endothelial cell density (ECD) requirements for age and ACD (refer to the “Minimum Endothelial Cell Density for Age and True ACD*” table below).6. Correctable (CDVA) to at least 20/40 in the eye to be treated; and absent of ocular pathology (except that myopic degeneration is allowed).7. Subjects must be able to achieve a minimum dilated pupil size of 7 mm (via use of mydriatic and/or cycloplegic eye drops) in each eye to be treated.8. Able to read, understand and provide written informed consent on the Institutional Review Board (IRB) approved Informed Consent Form (ICF).9. Able and willing to return for scheduled follow-up examinations after surgery. 
Exclusion Criteria (each eye to be implanted)
 
1. Younger than 21 or older than 45 years of age.2. With true ACD < 3.00 mm*.3. Anterior chamber angle less than Grade III as determined by gonioscopic examination.4. Do not meet the minimum ECD as defined in the “Minimum Endothelial Cell Density for Age and True ACD*” table below.5. Unstable or worsening nearsightedness.6. History or clinical signs of iritis/uveitis.7. Diabetic retinopathy.8. Glaucoma.9. History of previous eye surgery.10. Serious (i.e., life threatening), acute, chronic or systemic, non-ophthalmic disease or illness that would increase the operative risk, confound the outcome(s) of the study or which may preclude study completion.
--	---

	
 11. Progressive sight threatening disease or other previous or current ocular conditions, other than myopia, that may predispose for future complication. 12. Diagnosis of ocular hypertension (high eye pressure). 13. Insulin-dependent diabetes. 14. Pseudoexfoliation. 15. Pigment dispersion. 16. Spherical equivalent less than -3.0 D or greater than -15.0 D (in the spectacle plane) of nearsightedness; cylinder (spectacle plane) less than 1.0 D and greater than 4.0 D. 17. Pregnant or nursing women, or those who plan to become pregnant over the course of this clinical study or has another condition with associated fluctuation of hormones that could lead to refractive changes. 18. Involved in another clinical study or who may have been involved in a different clinical study within 30 days prior to this clinical study or will be involved in a different clinical study within 30 days of beginning this study. 
Minimum Endothelial Cell Density for Age and True ACD*
 
  
 Age	Minimum ECD ACD ≥ 3.0mm	Minimum ECD ACD ≥ 3.2mm	Minimum ECD ACD ≥ 3.5mm	
   
 21-25	3875 cells/mm²	3800 cells/mm²	3250 cells/mm²	
 
 26-30	3425 cells/mm²	3375 cells/mm²	2900 cells/mm²	
 
 31-35	3025 cells/mm²	2975 cells/mm²	2625 cells/mm²	
 
 36-40	2675 cells/mm²	2625 cells/mm²	2350 cells/mm²	
 
 41-45	2350 cells/mm²	2325 cells/mm²	2100 cells/mm²	
 
 >45	2075 cells/mm²	2050 cells/mm²	1900 cells/mm²	
  
 
*The true ACD is defined as the distance from the apex of the posterior corneal surface to the apex of the anterior crystalline lens surface. Many measuring devices provide an ACD measurement defined as the distance from the apex of the anterior corneal surface to the apex of the anterior crystalline lens surface. If the surgeon is using an instrument that measures from the anterior corneal surface, the thickness of the cornea must be subtracted to get the true ACD.
	Age	Minimum ECD ACD ≥ 3.0mm	Minimum ECD ACD ≥ 3.2mm	Minimum ECD ACD ≥ 3.5mm	21-25	3875 cells/mm ²	3800 cells/mm ²	3250 cells/mm ²	26-30	3425 cells/mm ²	3375 cells/mm ²	2900 cells/mm ²	31-35	3025 cells/mm ²	2975 cells/mm ²	2625 cells/mm ²	36-40	2675 cells/mm ²	2625 cells/mm ²	2350 cells/mm ²	41-45	2350 cells/mm ²	2325 cells/mm ²	2100 cells/mm ²	>45	2075 cells/mm ²	2050 cells/mm ²	1900 cells/mm ²
Age	Minimum ECD ACD ≥ 3.0mm	Minimum ECD ACD ≥ 3.2mm	Minimum ECD ACD ≥ 3.5mm																										
21-25	3875 cells/mm ²	3800 cells/mm ²	3250 cells/mm ²																										
26-30	3425 cells/mm ²	3375 cells/mm ²	2900 cells/mm ²																										
31-35	3025 cells/mm ²	2975 cells/mm ²	2625 cells/mm ²																										
36-40	2675 cells/mm ²	2625 cells/mm ²	2350 cells/mm ²																										
41-45	2350 cells/mm ²	2325 cells/mm ²	2100 cells/mm ²																										
>45	2075 cells/mm ²	2050 cells/mm ²	1900 cells/mm ²																										
Duration of treatment	Eligible subjects who are enrolled in the study will be seen for 11 study visits over the course of approximately 27 months.																												

Study parameters
	
The study will evaluate:
 
 • Rotational stability as determined through objective methods • Refractive and visual outcomes • Safety 
Primary effectiveness endpoint:
 
 • Rotation of less than or equal to five degrees between 18 and 24 months postoperative. 
Primary effectiveness endpoint success criteria:
 
 • At least 90% of the treated eyes rotate less than or equal to five degrees between 18 and 24 months postoperative (i.e., $\leq 10\%$ of eyes exhibit $>5^\circ$ rotation). 
Secondary effectiveness endpoints include:
 
 • Absolute rotation between visits. • Absolute rotation <5 degrees, <10 degrees, <20 degrees, and <30 degrees from the intended orientation at each visit. • Absolute rotation from the intended orientation at each visit. • Postoperative manifest refraction spherical equivalent and cylinder at each visit. 
Safety Endpoint:
 
 • Ocular AE rates assessed in implanted eyes. 
There are no prespecified performance targets for the secondary endpoints or the safety endpoint.


Statistical methods
	
Based on clinical experience with stabilization of lens rotation over time, we assume that between 18 and 24 months no more than 2% of eyes will exhibit rotation $>5^\circ$. Our null and alternate hypotheses are as follows:
 
H_0 (null hypothesis): $>10\%$ of eyes with $>5^\circ$ rotation H_a (alternative hypothesis): $\leq 10\%$ of eyes with $>5^\circ$ rotation
 
[REDACTED]
 
[REDACTED] Rates of rotation of the TICL of <10, <20 and <30 degrees from the intended orientation will be reported.
 
To allow for 10% attrition annually, a total of 124 subjects (up to 248 eyes, with 124 being primary) will be enrolled for assessment of the primary and secondary effectiveness/safety endpoints.
 
[REDACTED]
 
[REDACTED]

	
A sample of 100 eyes provides 94.9% power to reject the null hypothesis that >10% of eyes will exhibit >5° rotation. The two-sided 95.0% upper confidence limit of the proportion of eyes with >5° absolute rotation is ≤ 0.1. The null hypothesis will be rejected if the two-sided 95.0% upper confidence limit of the proportion of eyes with >5° absolute rotation between 18 and 24 months is ≤ 0.1. To allow for losses of 10% per year, a total of up to 124 primary eyes of 124 subjects will be enrolled.

--	---

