3.0 STUDY DESIGN

3.1 Description of Study Design

This is a prospective, multicenter, open-label, single arm, post-approval study. A total of 124 subjects (up to 248 eyes, with 124 being primary) who meet all eligibility criteria will be enrolled at 6-8 clinical sites in the United States (US).

It is intended that each enrolled subject will undergo bilateral implantation with the TICL. If only one eye of a given subject meets all of the inclusion and exclusion criteria, or the subject desires surgery in only one eye and that eye meets all of the inclusion and exclusion criteria, then that eye will be the primary eye. If both eyes of a given subject meet all of the inclusion and exclusion criteria, and the subject desires surgery in both eyes, then the eye with the greater magnitude of manifest refraction cylinder will be designated as the primary eye. If both eyes of a given subject meet all of the inclusion and exclusion criteria and the refractive cylinder of the eyes are equal, then the right eye will be designated as the primary eye.

A minimum of 14 subjects requiring a Toric ICL cylinder power of 3.5 or 4.0 D will be enrolled.

Study subjects will be followed at Day 0, Day 1, Week 1, Month 1, 3, 6, 12, 18, and 24 postoperatively (Refer to Appendix A).

STAAR will submit periodic study reports to FDA every six (6) months during the first two (2) years of the study and annually thereafter, unless otherwise specified by FDA. The first report will be submitted 6 months after the initial approval of this study protocol.

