3.2.3 Subject Discontinuation

A subject may be discontinued (at the discretion of the Investigator, the Sponsor and/or the IRB) prior to the final study visit for several reasons, including, but not limited to:

- voluntary withdrawal
- death
- surgical complication preventing implantation of the study lens in any eye
- explant of the study lenses

If both TICL lenses are explanted, a minimum of one post-explant visit should be completed to record safety measures for the subject (e.g., CDVA, cataract/lens evaluation, endothelial cell count, etc.) prior to subject discontinuation.

Prior to discontinuing a subject, every effort should be made to contact the subject, schedule a final study visit, and obtain as much follow-up data as possible.

Adverse events will be followed as described in Section 6.0. Subject withdrawals will be documented clearly on the source document and applicable CRF.

Only subjects who do not receive any study lenses MAY be replaced. Subjects who are discontinued from the study following treatment will not be replaced.

Discontinued subjects should be followed outside of the study protocol according to the Investigator's normal postoperative standard of care.

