3.3 Investigators

- The study will be conducted at approximately 6-8 clinical site(s) located in the US.
- The study will be conducted by Investigators who have prior clinical experience with the STAAR Surgical ICL and are determined by STAAR Surgical to be suitably qualified by training and experience to conduct this study in compliance with all applicable GCPs and FDA Federal Regulations. Sub-Investigators will be identified on the Device Investigator Agreement (DIA)/DOA (Delegation of Authority Log).

- Each clinical site will enroll approximately 20 subjects (40 eyes). In the event that selected sites do not meet full enrollment, the Sponsor may decide to increase enrollment as needed at other currently active sites and additional site(s) may be added to satisfy the enrollment requirements of the study.

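### Do the different statements of 124, together with a minimum of 14 high-cylinder subjects, leave enrolment without a workable end?

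*Combined protocol and SAP*

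**What the plan says.** The enrolment target is worded in three ways.

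- As a floor, in the synopsis row on centers and subjects: "The study will enroll and implant at least 124 eligible subjects".
- As a ceiling, in the synopsis design row: "Up to 124 subjects who meet all eligibility criteria will be offered consecutive enrollment in the study". The synopsis statistics row and Section 7.4 add: "To allow for losses of 10% per year, a total of up to 124 primary eyes of 124 subjects will be enrolled".
- As a fixed total, in Section 3.1: "A total of 124 subjects (up to 248 eyes, with 124 being primary) who meet all eligibility criteria will be enrolled". Section 7.5 and the synopsis statistics row also give a total of 124.

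Section 3.1 sets the high-cylinder minimum: "A minimum of 14 subjects requiring a Toric ICL cylinder power of 3.5 or 4.0 D will be enrolled". The synopsis repeats it.

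On sites, Section 3.3 says: "The study will be conducted at approximately 6-8 clinical site(s) located in the US". It expects about 20 subjects at each, and lets the sponsor raise enrolment at active sites or add sites when others fall short. On replacement, Section 3.2.3 says: "Only subjects who do not receive any study lenses MAY be replaced".

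Part of the synopsis statistics row is blacked out. Sections 3.1, 3.3, 7.4 and 7.5 show no blacked-out text and no rule for securing the 14.

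**The concern.** A floor, a ceiling and a fixed total agree only if the study enrols exactly 124. If the first 124 consecutive subjects include fewer than 14 who need a 3.5 or 4.0 D lens, something has to give: the minimum is missed, places are held back and the last subjects are no longer consecutive, or enrolment runs past 124 with no stated limit. The plan does not say which. The site plan seems to add to the doubt, since 6 to 8 sites at 20 each give 120 to 160 subjects.

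At stake would be how many people are implanted, whether the last ones are selected, and whether a stated minimum in a study required as a condition of approval is met. The final number also affects how many failing eyes the primary criterion tolerates.

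**Working it through.** **Inputs.** From the synopsis and Section 7.4: 100 evaluable eyes, 2% assumed failure rate, 10% loss per year. From Sections 7.1 and 7.5: a 10% null boundary, and success if the upper limit of a two-sided 95% exact binomial interval is at most 0.10. From Section 3.1: a minimum of 14. The share of candidates who need a 3.5 or 4.0 D lens is not in the documents, so a range of 5% to 20% is assumed.

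**1. The plan's own figures.** Two-year retention is 0.9 × 0.9 = 0.81. Then 100/0.81 = 123.46, rounded up to 124. Check: 124 × 0.81 = 100.4, but 123 × 0.81 = 99.6. The exact upper limit for x failures in n eyes is the 0.975 quantile of Beta(x + 1, n − x). At n = 100 at most 4 failures pass (upper limit 0.0993). P(X ≤ 4) with X ~ Binomial(100, 0.02) is 0.9492, the stated 94.9%. Both figures stand.

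**2. Does the final number matter to the test?** With n eyes observed and before any imputation:

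| Eyes | Failures allowed | Upper limit | Power at 2% | Type I error at 10% |
|---|---|---|---|---|
| 100 | 4 | 0.0993 | 94.9% | 2.4% |
| 112 | 4 | 0.0889 | 92.5% | 1.0% |
| 120 | 5 | 0.0946 | 96.6% | 1.6% |
| 124 | 5 | 0.0916 | 96.1% | 1.2% |
| 140 | 6 | 0.0909 | 97.7% | 1.1% |
| 160 | 8 | 0.0961 | 99.5% | 1.7% |

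The exact rule keeps the error below 2.5% at each size, and power exceeds 92% throughout. The power steps come from whole-number failure counts.

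**3. The high-cylinder minimum.** 14/124 = 11.3%. With share s and strictly consecutive enrolment, the number needing the lens is Binomial(124, s). If enrolment instead ran on until 14 were found, the total would be the larger of 124 and a negative binomial waiting time. If subjects not needing the lens were capped at 110 to keep the total at 124, the mean number turned away is the mean of that larger value minus 124.

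| Assumed share | P(at least 14 of 124) | Mean total if run on | Mean turned away under a 110 cap |
|---|---|---|---|
| 5% | 0.4% | 280 | 156 |
| 8% | 12% | 177 | 53 |
| 10% | 36% | 147 | 23 |
| 11.3% | 54% | 136 | 12 |
| 15% | 90% | 125 | 1 |
| 20% | 99.7% | 124 | 0 |

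**4. Could the choice of final number be steered by results?** Section 3.4 gives about 42 months in all and 27 per subject, leaving 42 − 27 = 15 months to recruit, or 124/15 = 8.27 subjects a month. The 24-month window opens at month 23 (Section 5.1). At that pace a run-on to 177 subjects ends at 177/8.27 = 21.4 months, before any primary outcome exists. Only near a 5% share (280/8.27 = 33.9 months) would some be known, and even then enrolment would end on a count of lens powers, not on rotation.

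**5. Are the statements compatible?** Exactly 124 subjects meets the floor, the ceiling and the total. In Section 7.4 the ceiling applies to primary eyes, and the subject count beside it is simply 124. Consecutive enrolment appears only in the synopsis; Section 3.1 gives the total and the minimum without it. Lens power is worked out before surgery and enrolment occurs on the operative day (Section 5.1.2), so the high-cylinder count can be tracked and places held.

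**The case for a change.** The strongest opposing case is that a stated minimum should not rest on an undocumented share. Even if the share equalled 11.3%, 124 consecutive subjects would miss it 46% of the time (100% − 54%). The flexibility in Section 3.3 covers sites that under-recruit, which is not the situation where 124 is reached with too few high-cylinder subjects. And if six sites stopped at 20 each, 120 × 0.81 = 97.2 evaluable eyes would remain; at 97 only 3 failures pass (upper limit 0.0877; 4 gives 0.1022) and power falls to 87.0%.

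The first part stands as an observation: the visible text does not say how the 14 are secured, and the synopsis phrase on consecutive order sits awkwardly with any enforced minimum. The second part is a fair reading of Section 3.3, but Section 3.1 leaves room to hold places without it. The third part does not stand. The site figures are approximate, 124/6 = 20.7 is about 20, Section 3.3 ties site enrolment to the study's requirements, and no section makes 120 or 160 a total. The failing-eye counts are also not the literal primary rule, because Section 7.6 imputes missing outcomes in the ITT analysis.

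**Conclusion.** No change is needed. The differing words around 124 are a clerical slip, mainly in the synopsis; every statement points to the same correctly derived number. How the 14 high-cylinder subjects are found is a recruitment procedure that the sponsor can run sensibly within Section 3.1, and the six-monthly reports to FDA give a regular occasion to raise a shortfall.

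The size of the quota problem is unknown, because it turns wholly on the assumed share: close to certain failure at 5%, close to none at 20%. Whatever the share, no visible endpoint or analysis in Sections 7.2 to 7.5 uses the 14 separately, so a shortfall would be a missed commitment to report and not a changed inference. A hard cap of 110 on other subjects would be a debatable trade: about 156 patients turned away and 156/8.27 = 19 more months at a 5% share, almost nothing at 15%. Replacing subjects who receive no lens could take the ITT set slightly above 124, which does no harm to the test.

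This rests on the visible text. A rule for the 14 may lie in the blacked-out part of the synopsis, and the conclusion does not depend on it.

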1.0 INTRODUCTION

The STAAR Visian® Toric Implantable Collamer® Lens (ICL) for Myopia (TICL) received FDA approval on September 13, 2018. The STAAR TICL is indicated for use in patients 21 – 45 years of age:

1. for the correction of myopic astigmatism with spherical equivalent ranging from -3.0 diopters (D) to \leq -15.0 D (in the spectacle plane) with cylinder (spectacle plane) of 1.0 D to 4.0 D.
2. for the reduction of myopic astigmatism with spherical equivalent ranging from greater than -15.0 D to -20.0 D (in the spectacle plane) with cylinder (spectacle plane) 1.0 D to 4.0 D.
3. with an anterior chamber depth (ACD) of 3.00 mm or greater, when measured from the corneal endothelium to the anterior surface of the crystalline lens and a stable refractive history (within 0.5 D for both spherical equivalent and cylinder for 1 year prior to implantation).
4. The Visian TICL is intended for placement in the posterior chamber (ciliary sulcus) of the phakic eye.

As a condition of FDA approval, STAAR is conducting a new enrollment post-approval study (PAS) in order to provide continued reasonable assurance of the safety and effectiveness of the TICL.

2.0 OBJECTIVE

The objective of this PAS is to evaluate the long term (i.e., 24 months) clinical performance of the TICL with respect to rotational stability, refractive and visual outcomes, and ocular adverse event (AE) rates.

3.0 STUDY DESIGN

3.1 Description of Study Design

This is a prospective, multicenter, open-label, single arm, post-approval study. A total of 124 subjects (up to 248 eyes, with 124 being primary) who meet all eligibility criteria will be enrolled at 6-8 clinical sites in the United States (US).

It is intended that each enrolled subject will undergo bilateral implantation with the TICL. If only one eye of a given subject meets all of the inclusion and exclusion criteria, or the subject desires surgery in only one eye and that eye meets all of the inclusion and exclusion criteria, then that eye will be the primary eye. If both eyes of a given subject meet all of the inclusion and exclusion criteria, and the subject desires surgery in both eyes, then the eye with the greater magnitude of manifest refraction cylinder will be designated as the primary eye. If both eyes of a given subject meet all of the inclusion and exclusion criteria and the refractive cylinder of the eyes are equal, then the right eye will be designated as the primary eye.

A minimum of 14 subjects requiring a Toric ICL cylinder power of 3.5 or 4.0 D will be enrolled.

Study subjects will be followed at Day 0, Day 1, Week 1, Month 1, 3, 6, 12, 18, and 24 postoperatively (Refer to Appendix A).

STAAR will submit periodic study reports to FDA every six (6) months during the first two (2) years of the study and annually thereafter, unless otherwise specified by FDA. The first report will be submitted 6 months after the initial approval of this study protocol.

